Chang Gung Memorial Hospital

NCT00952718

Date: 2019/10/31

Study Protocol:

Patients aged 40–80 years from the outpatient clinic of the Department of Pulmonology of a tertiary care medical centre who had bronchiectasis were eligible. Bronchiectasis was confirmed by clinical history, such as coughing, shortness of breath and exertional dyspnoea, pulmonary function tests and high-resolution computed tomography.

Those who were using steroids (including inhalation or oral), had recent exacerbation within six weeks, poor consciousness level and cerebrovascular or neuromuscular disorders were excluded. The eligible subjects were then randomly divided into either inspiratory muscle training or control groups. All technicians who performed the different measurements and assessed the outcomes were blinded to group allocation, and all measurements were performed at the beginning and end of the eightweek programme. The pulmonary function tests were performed in a pulmonary functional laboratory using a standard spirometer (Vitalograph, Serial Spirotrac, Buckingham, USA) according to the American Thoracic Society recommendations, and the measurements included parameters of forced vital capacity (FVC), FEV1 and maximum mid-expiratory flow. The best FVC measurement was recorded along with FEV1 and FEV1/FVC calculations.

After pulmonary function parameters were recorded, the bronchodilator test was used to check if the participant had a hypersensitive airway. The reversibility of the airway obstruction was defined as a 15% or greater improvement in FEV1 and at least a 200 mL increase in FEV1. None of our eligible patients showed a positive bronchodilator response. All measurements are presented as percentage predicted value. Baseline characteristics including height, weight, body mass index and duration of the disease, and the resting oxyhaemoglobin saturation (SpO2), lowest resting SpO2, Borg Scale during a 6-minute walking test, MIP, maximal expiratory pressure (MEP),and St George's Respiratory Questionnaire (SGRQ) were obtained in the Department of Respiratory Therapy.

SpO2 was measured using a finger pulse oximeter (FingerPrint, BCI International, Wisconsin,USA). Resting dyspnoea was quantified using the modified Borg Scale, which ranges from 0.5 to 10.27 The 6-minute walk work (6Mwork) value was calculated as body mass × distance covered during the 6-minute walking test. MEP was measured after maximal inspiration, while MIP was measured after maximal expiration with each subject seated and wearing a nose-clip. An experienced respiratory therapist strongly urged the subjects to make maximum

inspiratory and expiratory efforts at or near residual and total lung capacity, respectively.

Determinations were repeated until two technically satisfactory measurements were recorded, with the highest value used for calculations. St George's Respiratory Questionnaire has 76 items on symptoms (frequency and severity of respiratory symptoms), activity (activities caused or limited by breathlessness), and impact (social functioning and psychological disturbances resulting from airway disease) on daily life. The scores range from 0 to 100, with higher scores indicating poorer health. A mean change score of 4 units was defined as slightly efficacious treatment, 8 moderately efficacious, and 12 very effective treatment.

The inspiratory muscle training programme was started at an intensity of 30% MIP, and increased by 2 cmH2O each week. A pressure threshold device (Threshold IMT HS730, Resironics Inc, Cedar Grove, NJ, USA) was used. During training, patients were in a sitting position with a nose-clip and were instructed to place their lips around the mouthpiece, inhale with enough force to open the valve, exhale through the mouthpiece, and then continue inhaling and exhaling without removing the device from their mouths. Patients could take intermittent periods of rest if they felt uncomfortable. They were encouraged to perform inspiratory muscle training for 30 minutes per day, at least five days a week, for eight weeks. If the training sessions could not be completed due to increased resistance, the last part of the session was performed with the previous resistance setting.

Patients in the control group did not receive any training programme. Both groups were monitored by telephone call once or twice a week until the end of the study. The medication profiles were also recorded. No medication was altered during the study period.

The Institutional Review Board of Chang Gung Memorial Hospital, Kaohsiung Medical Center approved the study protocol and all patients provided informed consent.

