### **Statistical analysis**

Baseline characteristics were compared using the Student's t-test for continuous variables and Fisher's exact test for categorical variables.

Results are presented as absolute number (percentage) or mean (standard deviation) and adjusted for age by linear regression analysis.

The difference for each variable was compared with two-way repeated measures analysis of variance between the two groups and within each group. Paired sample T-tests were used for comparison within each group. A two-tailed P-value of less than 0.05 was considered significant. All statistical analyses were performed using the SPSS 14.0 software package (SPSS Inc., Chicago, IL, USA).

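### Does it matter that the Borg rating is described once as taken during the walk and once as taken at rest?

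*Combined protocol and SAP*

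**What the plan says.** Both mentions of the Borg Scale are in the Study Protocol section.

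- The list of assessments made in the respiratory therapy department runs: "the resting oxyhaemoglobin saturation (SpO 2 ), lowest resting SpO 2 , Borg Scale during a 6-minute walking test", followed by the respiratory pressures and the St George's questionnaire. The walk test is the only condition attached to the Borg item.
- The account of how the measurements were made starts with oximetry ("SpO 2 was measured using a finger pulse oximeter") and goes straight on to "Resting dyspnoea was quantified using the modified Borg Scale". It does not mention a rating during or after the walk.

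The same section says that measurements were made at the start and end of the eight-week programme, by technicians who did not know the allocation.

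The Statistical analysis section does not list its variables. It says "Baseline characteristics were compared using the Student's t-test for continuous variables" and "The difference for each variable was compared with two-way repeated measures analysis of variance", and adds paired tests within each group and an age adjustment by linear regression. It gives no separate rule for the Borg score.

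**The concern.** The methods text takes up the listed items in roughly the same order: saturation, Borg, pressures, questionnaire. A reader would therefore take its Borg sentence as the definition of the listed Borg item, yet the conditions differ. If only a resting rating was taken, the list carries the wrong label. If only a walk rating was taken, the methods sentence is wrong. If both were taken, each place leaves one out.

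Interpretation would be at stake. A fall in the score over eight weeks could be reported as less breathlessness on exertion or as less breathlessness at rest, and these are different claims about inspiratory muscle training. The Statistical analysis section covers every variable without naming any, so it cannot settle which was meant.

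**Working it through.** No arithmetic applies. The documents give no Borg mean, standard deviation, sample size or target difference, so there is no stated figure to reproduce. The check is to compare the passages and ask what would change under each reading.

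**Do the sentences conflict?** Neither says that its rating was the only one. A rating before the walk and another in the course of it would make both sentences true.

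**Is the list complete, so that silence about a resting Borg score counts as evidence?** No. The walk-work measure (body mass times distance) is introduced in the methods text and is absent from the list. The methods text therefore adds measures as well as describing listed ones, and it could add a resting Borg score in the same way. That the list has two saturation entries and one Borg entry says little about how many Borg ratings were taken.

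**Could the phrase about the walk apply more widely?** The list is loosely punctuated. The closing words may mark the whole saturation and Borg series as coming from the walk-test session, including values described as resting. A resting Borg score taken at that session would then fit both sentences. The text does not prove this reading, but does not exclude it.

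**What changes under each reading?**

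| Ratings taken | Analysis under the SAP | What the clarification alters |
|---|---|---|
| Rest only | Baseline t-test, repeated-measures ANOVA, paired tests, age adjustment | Label in the list |
| Walk only | The same | Label in the methods text |
| Both | The same, applied to each | Two labels |

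In no row does a test, a model, an estimate or a P-value change. Counting the tests that touch a Borg score would not measure the consequence either, since the number of tests does not show what a missing label costs.

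**Can the group comparison be biased?** The two visits and the blinded assessment apply to both groups. If the condition was the same in both groups and at both visits, the comparison is like with like whether the score was taken at rest or during the walk. The documents give no sign that the condition varied.

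**Is the answer recoverable?** The text is in the past tense and already reports patient findings, for example "None of our eligible patients showed a positive bronchodilator response". Collection therefore appears complete, and the investigators should know when each score was taken.

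**The case for a change.** The strongest case for acting is that an outcome should be defined by its condition of measurement, and that stating it costs only a few words. The protocol names exertional breathlessness separately when it describes the clinical history ("coughing, shortness of breath and exertional dyspnoea"). If two ratings exist, an unlabelled one could be reported as whichever looks better.

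Part of this stands. Rest and exertion are different conditions, the documents do not say which applies, and a reader given only these pages could not label a Borg result with certainty.

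The rest is weaker. The symptom phrase illustrates the history used to confirm bronchiectasis; it does not say how Borg scores are classified. As for choosing between ratings, the Statistical analysis section applies its comparison to every variable, so two recorded scores would both be analysed. The Borg score is not singled out as primary or as the basis of a decision, and no passage claims an effect on exertional breathlessness. The list's separate entry for a lowest saturation also described as resting is loosely worded too, but that is a different point and adds nothing here.

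**Conclusion.** The observation is accurate, but no change to the plan follows. This is incomplete labelling of a measurement that no passage gives a leading role. It is not a shown contradiction, because the two sentences agree if both ratings were taken. Clarifying it would record something the investigators already know. It would require no new measurement or analysis and would alter no computed result. The effect cannot be quantified from the documents, and no error rate or power figure depends on it.

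This rests on three assumptions: the rating condition was the same in both groups and at both visits; the investigators' records show when each score was taken; and each Borg result is reported with its condition, as is normal when results are tabulated. The documents contradict none of these. If a resting score were presented as evidence about breathlessness on exertion, that would be a fault in the report, and it could be judged there.

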### **Statistical analysis**

Baseline characteristics were compared using the Student's t-test for continuous variables and Fisher's exact test for categorical variables.

Results are presented as absolute number (percentage) or mean (standard deviation) and adjusted for age by linear regression analysis.

The difference for each variable was compared with two-way repeated measures analysis of variance between the two groups and within each group. Paired sample T-tests were used for comparison within each group. A two-tailed P-value of less than 0.05 was considered significant. All statistical analyses were performed using the SPSS 14.0 software package (SPSS Inc., Chicago, IL, USA).

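### The between-group test is a repeated measures ANOVA with no named treatment term and no adjustment for the outcome's baseline; ANCOVA on data already collected would usually be more precise

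*Combined protocol and SAP*

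**What the plan says.** The protocol describes a randomised two-group trial of inspiratory muscle training against no training, with two measurement occasions: "all measurements were performed at the beginning and end of the eightweek programme". Each outcome therefore has one baseline/week-8 pair.

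The Statistical analysis section gives three separate statements about outcomes:

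- Between groups: "The difference for each variable was compared with two-way repeated measures analysis of variance between the two groups and within each group".
- Within groups: "Paired sample T-tests were used for comparison within each group".
- Adjustment, in a sentence on how results are presented: "mean (standard deviation) and adjusted for age by linear regression analysis".

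The significance rule is "A two-tailed P-value of less than 0.05 was considered significant". For the SGRQ, the protocol defines benefit as a change: "A mean change score of 4 units was defined as slightly efficacious treatment". No described model includes the outcome's own baseline value as a covariate.

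**The concern.** A two-way repeated measures ANOVA with factors group and time has three terms: group, time and group-by-time. Only group-by-time estimates the between-group difference in change, and the plan does not name it. This raises three issues.

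1. **Precision.** On the natural reading the treatment test is group-by-time, which with two visits is a change-score test. It ignores the information that an adjustment for the baseline value would use.
2. **Which term.** The wording does not exclude the group main effect, which averages baseline with week 8 and so dilutes the effect. Placing within-group comparisons beside it also makes it easy to read significance in the training arm alone as evidence of benefit.
3. **Which model.** Age adjustment is by linear regression and is not said to be part of the ANOVA. A reader cannot tell whether the age-adjusted results and the P-values come from the same model.

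The first issue concerns efficiency, not bias. It matters most if the arms are small and r is low or moderate.

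**Working it through.** **Inputs.** From the documents: two randomised groups, two visits, two-sided 5% level, age as the only adjustment. Not in the documents, so assumed: 1:1 allocation, SD of 1 at both visits, n per arm, true effect d (in SD units) and correlation r. There is no stated power figure to reproduce.

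**Step 1: what the ANOVA tests.** With two visits, the group-by-time F equals the square of the two-sample t on change scores. A numerical check on a simulated dataset gave 6.423 for both.

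**Step 2: variance per patient, large samples.**

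- Change score (group-by-time): 2(1−r)
- ANCOVA on baseline: 1−r²
- Ratio: (1−r²)/[2(1−r)] = (1+r)/2

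| r | ANCOVA / change variance | Patients needed by change score, relative to ANCOVA |
|---|---|---|
| 0.3 | 0.65 | 1/0.65 = 1.54 |
| 0.5 | 0.75 | 1/0.75 = 1.33 |
| 0.7 | 0.85 | 1/0.85 = 1.18 |
| 0.9 | 0.95 | 1/0.95 = 1.05 |

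**Step 3: power from the noncentral t, d = 0.6.** Noncentralities are d/√[(2/n)·2(1−r)] with 2n−2 df for group-by-time, and d/√[(2/n)(1−r²)] with 2n−3 df for ANCOVA with baseline only. At n=20 and r=0.5, for example, they are 0.6/√0.1 = 1.90 and 0.6/√0.075 = 2.19.

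| n per arm | r | Group-by-time | ANCOVA |
|---|---|---|---|
| 20 | 0.3 | 34.6% | 49.1% |
| 20 | 0.5 | 45.6% | 56.9% |
| 20 | 0.7 | 66.5% | 73.5% |
| 20 | 0.9 | 98.5% | 98.9% |
| 50 | 0.3 | 70.9% | 87.6% |
| 50 | 0.5 | 84.4% | 92.9% |
| 50 | 0.7 | 97.0% | 98.6% |

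**Step 4: the model actually recommended.** Adding age as a second covariate costs another degree of freedom. Simulation at 20 per arm and d = 0.6 (8,000 trials per r, age assumed unrelated to outcome) gave:

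| r | Power, group-by-time | Power, ANCOVA with baseline and age | Mean 95% CI width, ANCOVA / change score |
|---|---|---|---|
| 0.3 | 35.6% | 48.2% | 1.247/1.503 = 0.83 |
| 0.5 | 46.1% | 55.1% | 1.135/1.270 = 0.89 |
| 0.7 | 67.0% | 71.7% | 0.936/0.984 = 0.95 |
| 0.9 | 98.5% | 98.4% | 0.571/0.570 = 1.00 |

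Mean estimates for a true 0.60 were 0.60 to 0.61 under both methods, so neither is biased.

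**Step 5: the other terms.** If the group main effect were taken as the treatment test, it would estimate d/2 because the groups do not differ at baseline in expectation. The noncentrality is (d/2)/√[(2/n)(1+r)/2]. At 20 per arm and d = 0.6 the mean estimate is 0.30, and power is 20.9%, 18.7%, 17.1% and 15.8% at r = 0.3, 0.5, 0.7 and 0.9.

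For the within-group route, assume no treatment effect, a change of 0.4 SD common to both arms, r=0.7 and 20 per arm. In simulation, exactly one of the two paired t-tests is significant in 48% of trials, and the time main effect in 89%.

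**The case against.** The strongest counter-argument is that, on the natural reading, nothing is wrong. The plan compares differences, measurements are taken before and after, and SGRQ benefit is defined as a change, so group-by-time is the obvious treatment term. That test is valid and unbiased, and preferring ANCOVA is a matter of efficiency. The halved effect belongs only to a less likely reading, and the paired t-tests are confined to within-group comparison by their own sentence. All of this stands, and it limits the point to precision and clarity.

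The gain is also uncertain for this trial. The large-sample ratio and the one-covariate power figures overstate what the two-covariate model delivers at 20 per arm: 9 points of power instead of 11 at r=0.5, and under 5 instead of 7 at r=0.7. In very small trials with very high r the recommended model can be worse. At 10 per arm and r=0.9, simulation gives a mean CI width ratio of 1.04, with power falling from 81.1% to 77.7%; at 15 per arm the width ratio is 1.015. Patients with a recent exacerbation were excluded and medication was unchanged, so a high r is plausible for some outcomes. This also stands, and it is why the claim is that ANCOVA is *usually* more precise. But the same rule covers every outcome, from spirometry and respiratory pressures to walking work and the SGRQ, and these need not all correlate so highly.

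Finally, the document is written in the past tense, so replacing a sentence could misdescribe an analysis already done. That affects how the fix is made, not whether the point holds.

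**Conclusion.** The concern holds and should be fixed. The described between-group analysis is, on its natural reading, a valid change-score test that usually sacrifices precision. With 20 per arm, baseline-and-age ANCOVA would shorten the mean confidence interval by about 17% at r=0.3, 11% at r=0.5 and 5% at r=0.7, and not at all at r=0.9. These figures assume equal SDs, 1:1 allocation and age unrelated to outcome. Sample size and r are not in the documents, so the gain in this trial can be given only as a range, and it may reverse slightly with very small arms and very high r. Separately, the plan leaves open which ANOVA term tests training and whether age is in that model. Neither the group main effect nor the paired t-tests estimates the between-group difference in change.

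**What to change.** If the analysis has not been run, replace the ANOVA sentence with:

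> For each outcome the groups are compared by ANCOVA of the week-8 value on randomised group, with the baseline value of that outcome and age as covariates. The adjusted between-group difference, its 95% CI and its P-value are reported from this one model. The ANOVA group main effect is not used as a test of training, and within-group paired t-tests are descriptive only.

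If the analysis has been run, as the past tense suggests, leave the description of what was done accurate. State that group-by-time is the treatment term, if that is what was used, and whether age was in that model. Add the ANCOVA as a reanalysis labelled as not pre-specified. If the ANOVA is kept as the main analysis, the same two clarifications are the minimum.

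The cost is small: baseline values and age are already collected, and two degrees of freedom are used, one per covariate. Where results exist, the real cost is the reanalysis and its reporting.

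### The stated tests use only patients measured at both visits, and the plan gives no analysis set or missing-data method, so any missing week-8 value in either arm takes a randomised patient out of the comparison

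*Combined protocol and SAP*

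**What the plan says.** The Study Protocol section describes a two-arm randomised design: "The eligible subjects were then randomly divided into either inspiratory muscle training or control groups". On timing it says that "all measurements were performed at the beginning and end of the eightweek programme", so there are two outcome visits and none in between.

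The Statistical analysis section then names two outcome tests: "The difference for each variable was compared with two-way repeated measures analysis of variance between the two groups and within each group", and "Paired sample T-tests were used for comparison within each group". It also mentions age adjustment by linear regression, without detail, and SPSS 14.0, without naming the procedure.

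The arms differ in burden. For trainees: "They were encouraged to perform inspiratory muscle training for 30 minutes per day, at least five days a week, for eight weeks". For controls: "Patients in the control group did not receive any training programme". Both groups were telephoned until the study ended.

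The document does not give an analysis set, an intention-to-treat or per-protocol statement, a missing-data method, a sensitivity analysis, a number randomised or analysed, or a dropout figure. It does not say whether a patient who stops training is still measured at week 8.

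**The concern.** This is more than a missing detail, because the named methods settle by default what the plan leaves unsaid. Classical repeated measures ANOVA on two visits and the paired t-test both need two values per patient. A patient with only a baseline value contributes to neither, and no other analysis is planned that would keep that patient in.

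Unequal loss is plausible because only one arm carries a daily programme with weekly increases in resistance, and the protocol itself foresees sessions that cannot be completed. If loss differs between arms and is related to severity or response, the comparison is no longer between the groups that were randomised, and nothing in the plan would reveal it.

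**Working it through.** The document states no sample size, SD, dropout or expected effect, so there is no figure of the plan's own to reproduce. All loss rates, correlations and effects below are assumptions.

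**1. What the named tests do with a missing end value.** Simulated two-visit data, 20 patients per arm, 4 training-arm end values removed:
- Group-by-time F from the split-plot sums of squares = 7.816.
- Squared t from a two-sample t-test on change scores = 7.816.
- Randomised 40, analysed 36. The paired t-test in the training arm uses 16 of 20.

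The between-group test is therefore a change-score test on patients with both values. The same deletion would apply to a control without an end value.

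**2. Illustration on the SGRQ scale.** The Study Protocol grades mean changes of 4, 8 and 12 units. Let d be the share of the training arm without an end value, with the control change set to 0 and fully observed.

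Overstatement = d × (mean change in those kept − mean change in those missing)

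| d | kept 8, missing 0 | kept 8, missing 4 |
|---|---|---|
| 0% | 0 | 0 |
| 5% | 0.4 | 0.2 |
| 10% | 0.8 | 0.4 |
| 20% | 1.6 | 0.8 |
| 30% | 2.4 | 1.2 |

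At d = 20% with no gain in those missing, the observed-case effect is 8 and the all-randomised effect is 8 − 1.6 = 6.4, which falls below the 8-unit grade.

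**3. Stopping training is not the same as missing the visit.** Suppose 20% stop and gain 0 while the rest gain 8, so the all-randomised effect is 0.8 × 8 = 6.4.
- All stoppers attend week 8: observed-case 6.4, no bias.
- Half attend: 6.4 / 0.9 = 7.1.
- None attend: 6.4 / 0.8 = 8.0.

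**4. Direction of bias under a null effect.** Loss is in the training arm only, at 21%, with a logistic slope of 1 per SD; higher scores mean better. ρ is the baseline-to-end correlation. In simulation, the patients kept average 0.18 SD above the full group on whichever variable drives the loss.
- *Poor responders leave* (loss driven by change): bias = +0.18 SD of change. At 11% loss it is about 0.10.
- *Sicker trainees leave* (loss driven by baseline): those kept start 0.18 SD higher and regress to the mean, so bias = −(1 − ρ) × 0.18. This is −0.09 at ρ = 0.5 and −0.05 at ρ = 0.7, in SD of the outcome at one visit. At ρ = 0.5 that equals the SD of change; at ρ = 0.7 the SD of change is √(2 × 0.3) = 0.77 of it.

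**5. What baseline adjustment removes.**
- Baseline-driven loss: the bias falls to about 0 in simulation.
- Outcome-driven loss: the bias becomes roughly 0.18 × (1 + ρ)/2, that is 0.14 at ρ = 0.5 and 0.15 at ρ = 0.7. Most of it remains.
- Precision: variance relative to the change-score analysis = (1 − ρ²) / [2(1 − ρ)] = (1 + ρ)/2, that is 0.75 at ρ = 0.5 and 0.85 at ρ = 0.7.

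**The case against.** The strongest reply is that no missing value is shown. The document reports no dropout, places no condition of continued training on the week-8 measurement, and describes telephone contact with both groups to the end. If everyone was measured, the named tests use everyone and the bias is zero. That stands, and it makes the point conditional.

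A reader might infer three stronger things that the document does not support:
- *That trainees who stop are dropped.* Deletion follows a missing measurement. A stopper who attends week 8 stays in, and a control who misses it leaves. The rule for hard sessions, "If the training sessions could not be completed due to increased resistance, the last part of the session was performed with the previous resistance setting", concerns resistance within a session and is not a withdrawal rule.
- *That the bias favours training.* It does if poor responders leave the training arm. Loss of sicker trainees biases the change-score comparison the other way.
- *That "No medication was altered during the study period" points to hidden exclusions.* Its plainest reading is that nobody's medication changed. It is no evidence about who was analysed.

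It is also fair to say that a mixed model does not cure outcome-driven loss. With only two visits, a patient with just a baseline value informs the baseline mean and says little about change. This stands too, and it is why the model alone is not a sufficient remedy.

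Finally, the SPSS procedure is not named, so complete-case deletion is a property of the classical tests as written and not a rule the plan states.

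**Conclusion.** The point holds in conditional form. The plan's tests give an observed-case estimate whenever a week-8 value is missing in either arm, and the plan names nothing to detect or correct this. The size cannot be determined from the document and may be zero. Under the assumptions in the working (one-arm loss of 21%, logistic slope 1 per SD, ρ of 0.5 to 0.7), it ranges from about +0.18 SD of change to about −0.09 SD, with the sign set by who is lost. On the SGRQ illustration the overstatement is 0 to 2.4 units for 0 to 30% missing, if those missing gain nothing and those kept gain 8. This is a worthwhile and inexpensive improvement to the plan. It does not show that the comparison is biased.

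**What to change.** - State that all randomised patients are analysed in their assigned group, and report numbers randomised and analysed by arm for each outcome.
- Replace the two-way ANOVA with a mixed model for both visits: common baseline mean, arm-by-time effect, and age. This keeps patients with only a baseline value, removes bias from loss that depends on baseline, and improves precision.
- Add one sensitivity analysis in which training-arm patients without a week-8 value are given the control-arm mean change. This is the analysis step that addresses outcome-driven loss, which the mixed model leaves largely in place.
- If follow-up is still open, seek the already planned week-8 measurement from every patient, whether or not they still train. The document is written in the past tense, so this may no longer be possible; the other steps still are.

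The cost is SAP wording and modest analysis time, plus some effort to bring patients to an existing visit if follow-up continues. The estimate may move in either direction.

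### No between-arm analysis is named as deciding efficacy: within-arm paired t-tests share the ANOVA's P<0.05 rule, and SGRQ change is graded without reference to control

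*Combined protocol and SAP*

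**What the plan says.** The design is a two-arm randomised comparison: "The eligible subjects were then randomly divided into either inspiratory muscle training or control groups". Measurements are taken twice, at the start and end of eight weeks (Study Protocol).

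The Statistical analysis section then lists, without ranking them:

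- an ANOVA: "The difference for each variable was compared with two-way repeated measures analysis of variance between the two groups and within each group";
- within-arm tests: "Paired sample T-tests were used for comparison within each group";
- an age adjustment whose link to the ANOVA is not stated: "Results are presented as absolute number (percentage) or mean (standard deviation) and adjusted for age by linear regression analysis";
- one threshold for everything: "A two-tailed P-value of less than 0.05 was considered significant".

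For the SGRQ, the Study Protocol section adds: "A mean change score of 4 units was defined as slightly efficacious treatment, 8 moderately efficacious, and 12 very effective treatment". It does not say whether that change is measured against control.

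The plan does not name the group-by-time term. It says neither that the within-arm results count as efficacy nor that they are descriptive.

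**The concern.** Because allocation is random, the effect of training is the difference between arms. A paired t-test is valid for its own null hypothesis of no change in that arm. However, the paired tests, the ANOVA time term and a single arm's SGRQ change all respond to anything that moves both arms, such as learning or effort. Maximal pressures depend on effort ("An experienced respiratory therapist strongly urged the subjects to make maximum" efforts), and both arms were telephoned once or twice a week, so some shared change is possible.

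As written, an efficacy statement could rest on a within-arm P-value, or on an SGRQ grade reached in the training arm alone, and make no use of the control group. A second, smaller point is precision. The group-by-time term handles baseline only by subtraction. The baseline value is already collected and could be used as a covariate, which usually gives a tighter estimate.

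**Working it through.** **Inputs from the documents.** Two-sided alpha of 0.05, two arms, two time points, and SGRQ thresholds of 4, 8 and 12 units. There is no sample size, power, SD or correlation, so there is no design figure to reproduce.

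**Assumptions.** n = 15 or 20 per equal arm; baseline to 8-week correlation r; change d shared by both arms, in SDs of the change score; equal variance s² at both visits; no treatment effect in steps 1 to 3.

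**1. Significant in training, not in control.** Let p be the power of one arm's paired t-test (noncentral t, noncentrality d√n, n−1 df). The arms are independent with the same true change, so the pattern has probability p(1−p), which cannot exceed 0.25.

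| d | p, n=15 | p(1−p) | p, n=20 | p(1−p) |
|---|---|---|---|---|
| 0 | 0.050 | 0.0475 | 0.050 | 0.0475 |
| 0.2 | 0.112 | 0.099 | 0.136 | 0.118 |
| 0.3 | 0.192 | 0.155 | 0.247 | 0.186 |
| 0.5 | 0.438 | 0.246 | 0.564 | 0.246 |

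At d = 0, the benefit direction alone accounts for 0.025 × 0.95 = 0.024. The maximum of 0.25 is reached near d = 0.54 (n=15) and 0.46 (n=20).

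**2. ANOVA time term.** Noncentrality d√(2n), 2n−2 df. At d = 0.3 this is 1.64 (n=15) and 1.90 (n=20), so the term is significant in 35.5% and 45.6% of trials with no treatment effect.

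**3. Between-arm tests.** With two visits, group-by-time is the two-sample t-test on change scores, so shared change cancels. In simulations of 100,000 trials per setting (n = 15 and 20; r = 0.5 and 0.8; d = 0, 0.3 and 0.5), rejection was 0.049–0.051 for group-by-time and 0.048–0.052 for ANCOVA.

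**4. SGRQ.** If both arms truly improve by 4 units, the training arm reaches the lowest grade with probability 0.50 although the between-arm difference is zero. If both improve by 2 units, with an assumed SD of change of 10 and n = 15, z = (4−2)/(10/√15) = 0.77 and the probability is 0.22. It ranges from 0.09 to 0.34 over SD 8–15 and n 10–30.

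**5. ANCOVA against group-by-time.** The residual variance ratio is s²(1−r²) / [2s²(1−r)] = (1+r)/2, that is 0.75 at r = 0.5 and 0.90 at r = 0.8. After paying for two covariates (baseline, and age taken as unrelated to outcome), with N = 2n:

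CI width ratio = √[(1+r)/2 × (1 + 2/(N−5))] × t(.975, N−4)/t(.975, N−2)

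- n=15, r=0.5: √(0.75 × 1.080) × 2.0555/2.0484 = 0.903
- n=20, r=0.5: √(0.75 × 1.057) × 2.0281/2.0244 = 0.892
- r=0.8: 0.989 (n=15) and 0.977 (n=20)
- r=0.9: 1.016 (n=15) and 1.004 (n=20)

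The ratio reaches 1 at r ≈ 0.84 (n=15) and r ≈ 0.885 (n=20).

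**The case against.** The best defence is that nothing invalid is planned. The ANOVA comes first, covers every variable and is the only outcome test described as between groups. The paired tests are expressly confined to each arm, and no sentence lets them decide efficacy. On that reading only a label is missing, and naming group-by-time would supply it. This stands in part: the group-by-time test is valid. But the ANOVA also yields group and time terms under the same threshold, and the plan does not say which is to be read.

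The error rates in steps 1 and 2 depend on a decision rule the plan does not state and on shared change it does not document. This also stands. Encouragement that is the same at both visits creates no change. Recent exacerbations were excluded, and "No medication was altered during the study period". Shared change may be small, and at d = 0 the pattern rate is not inflated.

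The SGRQ sentence sits in the description of the instrument and could be a guide to the scale. That is a possible reading, but it attaches efficacy of treatment to a change with no stated comparator.

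Finally, the text is in the past tense, so replacing a planned test with ANCOVA adds flexibility late, for a gain of 1–2% in CI width at r = 0.8. This is a real cost. Reporting group-by-time alongside limits it. Nor does naming one analysis settle which outcome is primary.

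**Conclusion.** The concern holds. The plan names no between-arm analysis as the basis for efficacy, and its one stated efficacy grading makes no reference to control. The defect lies in designation and interpretation; a valid test is present. It should be corrected.

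The text alone supports that conclusion. The sizes are illustrations. At an assumed 15 to 20 per arm with no treatment effect, the misleading within-arm pattern occurs in 4.8% of trials per outcome with no shared change, 10–12% at 0.2 SD, 15–19% at 0.3 SD, and never more than 25%. ANCOVA narrows the CI by about 10–11% at r = 0.5 and 1–2% at r = 0.8, and gives no gain near r = 0.9. The case for a single deciding between-arm analysis does not depend on r.

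**What to change.** Amend the Statistical analysis section, and the SGRQ sentence in the Study Protocol section, to state that:

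- efficacy statements rest only on the between-arm difference from ANCOVA of the 8-week value on group, baseline value and age, reported with a 95% CI;
- the ANOVA group-by-time term is reported as supportive and does not decide efficacy;
- the 4/8/12-unit SGRQ grades are read against the between-arm difference and its CI;
- the paired t-tests, the ANOVA time term and each arm's mean change are descriptive.

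Say how the existing age adjustment relates to this model. If the change is made after the data have been seen, say so and show both between-arm analyses.

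The cost is SAP wording and reanalysis of data already collected. Within-arm P-values no longer support efficacy claims. ANCOVA spends two residual degrees of freedom, so at r near 0.9 the CI is no narrower than from group-by-time (ratio 1.02 at 15 per arm, 1.00 at 20).
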